3.3. Study Definitions and Derived Variables

For individual subjects, fold rise will be calculated as the ratio of: $\frac{\text{post-vaccination titer}}{\text{pre-vaccination titer}}$, where pre-vaccination value is always the result obtained at Day 1, prior to the priming vaccination.

HAI Seroconversion is defined as either a pre-vaccination HAI titer <10 and a post-vaccination HAI titer ≥ 40 or a pre-vaccination HAI titer ≥ 10 and a minimum four-fold rise in post-vaccination HAI titer [5].

Neut Seroconversion is defined as either a pre-vaccination Neut titer <1:10 and a post-vaccination Neut titer $\geq 1:40$ or a pre-vaccination Neut titer $\geq 1:10$ and a minimum four-fold rise in post-vaccination Neut antibody titer.

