- A urine or serum pregnancy test will be performed locally by the site within 24 hours prior to the second study vaccination for all women of childbearing potential. Results must be negative and known prior to the second study vaccination.
- Approximately 10 mL of venous blood will be collected immediately prior to the second study vaccination for clinical safety labs (WBC, Hgb, PLT, ALT, T. Bili, Cr) to be performed by the central (clinical) laboratory. The results from these evaluations will not be available or reviewed prior to the second study vaccination.
- Approximately 15 mL of venous blood will be collected immediately prior to the second study vaccination for serological assays.
- Approximately 32 mL of venous blood will be collected immediately prior to the second study vaccination for cellular immunology assays.
- Approximately 16 mL of venous blood will be collected immediately prior to the second study vaccination for future research.
- Pre-administration reactogenicity assessments will be performed immediately prior to the second study vaccination to establish baseline.
- Subjects will then receive one- 0.5 mL dose of study vaccine via a single IM injection into the deltoid muscle of the subjects' preferred arm. The second study vaccination may be given in the same preferred arm as long as there is no interference with the reactogenicity assessment. The site of injection (right or left arm) and time of study vaccine administration to the subject will be recorded on the appropriate DCF. Subjects will be observed in the clinic for at least 20 minutes after the second study vaccination.

The second study vaccination site will be examined, post-administration reactogenicity assessments will be performed, and any AE/SAEs will be recorded on the appropriate DCF prior to discharge from the clinic.

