11.4.3 Sample Size

This study is planned to enroll up to 180 subjects. The sample size for this study was selected to obtain preliminary estimates in a time critical manner. While this study is not designed to test any specific null hypothesis, the following illustrates the precision and power that are available for select estimates and comparisons of interest.

[Table 12](#) indicates the probability of observing one or more safety events, such as solicited injection site or systemic reactogenicity events or an unsolicited non-serious AE of a particular type for a single treatment arm (N=30), or in the trial as a whole (N=180).

Table 12: Power (%) to Detect Safety Events

Event Frequency	N=30	N=180
≥10% Very Common	95	>99
≥1% Common	26	83
≥0.1% Uncommon	2	16
≥0.01% Rare	<1	1

Binomial confidence intervals (CI) are widest (have the least precision) when the response rate is 50%. [Table 13](#) is presented to indicate the worst-case scenario for precision of observed exact (Clopper-Pearson) binomial confidence intervals.

Table 13: Precision of Binomial Confidence Intervals

N	95% CI
30	31-69
180	42-58

[Table 14](#) illustrates the minimum detectable differences in the proportion of subjects responding (e.g. attaining seroconversion or a titer $\geq 1:40$) between any two treatment arms (N=30) using a two-sided Likelihood Ratio Test and $\alpha = 0.05$. It is assumed that up to 10% of subjects (N=3) will be excluded from the per protocol analysis. Seroconversion rates of 10% to 50% are considered.

Table 14: Minimum Detectable Difference in Proportion Responders

N per Group	Proportion Responders in Comparator Group A	80% Power	
		Minimal Detectable Difference	Proportion Responders in Comparator Group B
N=27	0.10	0.32	0.42
	0.20	0.35	0.55
	0.30	0.38	0.68
	0.40	0.37	0.77
	0.50	0.34	0.84

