3. STUDY OBJECTIVES AND ENDPOINTS

3.1. Study Objectives

3.1.1. Primary

Safety:

- To assess the safety and reactogenicity of 2013 and 2017 A/H7N9 IIVs given with or without AS03 adjuvant following receipt of each study vaccine.

Immunogenicity:

- To assess the serum hemagglutination inhibition (HAI) and neutralizing (Neut) antibody responses following receipt of the second study vaccine.

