4. INVESTIGATIONAL PLAN

4.1. Overall Study Design and Plan

DMID Protocol 17-0078 follows a Phase II randomized, partially-blinded study design enrolling males and non-pregnant females aged 19 to 50 years of age, inclusive, who are in good health as determined by medical history and physical examination, and meet all eligibility criteria, including erythrocyte sedimentation rate (ESR), hematology, and biochemistry parameter within acceptable range, and negative urine or serum pregnancy test (for females). This clinical trial is designed to assess the safety, reactogenicity and immunogenicity of one or two vaccinations of monovalent inactivated split influenza 2013 and 2017 A/H7N9 virus vaccines (2013 and 2017 A/H7N9 IIVs) manufactured by Sanofi Pasteur (SP), administered intramuscularly at different dosages (3.75 or 15 mcg of HA per dose), given with or without AS03 adjuvant manufactured by GlaxoSmithKline Biologicals (GSK), using different heterologous and homologous prime-boost vaccination schedules.

Subjects will be randomly assigned to 1 of 6 study groups with equal allocation 1:1:1:1:1:1 (see [Table 1](#)). Subjects assigned to Groups 1, 2, and 3 will receive an adjuvanted 2013 A/H7N9 IIV on Day 1 while those in Groups 4, 5, and 6 receive an adjuvanted 2017 A/H7N9 IIV on Day 1. Subjects assigned to Groups 1 and 4 will return approximately 21 days after their first vaccination to receive an adjuvanted 2017 A/H7N9 IIV. Subjects assigned to Groups 2,3,5, and 6 will return approximately after 120 days to receive their second vaccination of 2017 A/H7N9 IIV with or without AS03.

Reactogenicity will be measured by the occurrence of solicited injection site and systemic reactions from the time of each study vaccination through 7 days after each study vaccination. Unsolicited non-serious AEs will be collected from the time of each study vaccination through approximately 21 days after each study vaccination. SAEs and MAAEs, including NOCMCs and PIMMCs, will be collected from the time of the first study vaccination through approximately 12 months after the last study vaccination. Clinical laboratory evaluations for safety will be performed on venous blood collected prior to each study vaccination and approximately 7 days after each study vaccination.

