8.3.2. HAI and Neut Regression Modeling

Regression modeling will be utilized to test for the effect of treatment variables i.e. prime boost combination (*PrimeBoost*), Boost dose (*BoostDose*), and interval between vaccinations (*Interval*), on immune response. Logistic regression will be fit for the seroconversion outcome. If the available titer data meet the required assumptions of normality after log transformation, multiple linear regression will be fit to log-transformed titers. Separate models will be fit for each assay (HAI, Neut), each strain (2013 A/H7N9, 2017 A/H7N9) and each time point (Day 22 post vaccination 1, Day 22 post vaccination 2, Day 181 post vaccination 2). All models will be fit with a similar structure for *PrimeBoost*, *BoostDose*, *Interval*, and covariates, for the PP population. The treatment variables will be defined as *PrimeBoost* (homologous, heterologous), *BoostDose* (3.75 mcg+AS03, 15 mcg), and *Interval* (21 days, 120 days). All models will be fit with and without adjustment for the following covariates (*Z*): age in years, sex (female, male), BMI (<30, ≥ 30), and prior receipt of seasonal influenza vaccine in the current season (did not receive 2018-2019 seasonal influenza vaccine, received 2018-2019 seasonal influenza vaccine) (did not receive 2016-2017 or 2017-2018 seasonal influenza vaccines, received 2016-2017 and/or 2017-2018 seasonal influenza vaccine). The models as shown below assume a linear relationship between age in years and both probability of seroconversion and GMT. The validity of this assumption will be assessed prior to analysis and, if the relationship between age and response is found to be non-linear, adjustments will be made to model parameters to satisfy regression assumptions. Modeling assumptions will be checked using standard diagnostic methods (e.g., using the INFLUENCE option in PROC LOGISTIC or PROC GLM). Parameter estimates and odds ratio estimates for the logistic models will be presented for the 2013 and 2017 A/H7N9 strains without covariate adjustment in Table 64, Table 65, Table 66, Table 67, and with covariate adjustment in Table 68, Table 69, Table 70, Table 71. Parameter estimates for the multiple linear regression models will be presented for the 2013 and 2017 A/H7N9s strain without covariate adjustment in Table 72, Table 73, Table 74, Table 75, and with covariate adjustment in Table 76, Table 77, Table 78, Table 79.

Model 1A: Logistic Regression (without covariate adjustment):

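### The log-titer model for boost formulation omits the titer measured just before dose 2: a free gain in precision, not a bias to correct

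*SAP*

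**What the plan says.** The primary immunogenicity objective in SAP 3.1.1 is "To assess the serum hemagglutination inhibition (HAI) and neutralizing (Neut) antibody responses following receipt of the second study vaccine". SAP 4.1 allocates the arms equally: "Subjects will be randomly assigned to 1 of 6 study groups with equal allocation 1:1:1:1:1:1". SAP Table 1 shows that Groups 2 and 3 get the same prime and the same interval and differ only in the second injection. The same is true of Groups 5 and 6. Under SAP 4.4.6, subjects and assessors do not know antigen or dosage, though they know the interval.

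Protocol 8.2.7 states for every arm: "Approximately 15 mL of venous blood will be collected immediately prior to the second study vaccination for serological assays". This is Day 22 in Groups 1 and 4 and Day 121 in Groups 2, 3, 5 and 6. Titers at that visit are secondary endpoints (SAP 3.2.2). They appear with confidence intervals in Tables 24–31 and in the GMT plots (Figures 6–9), and individually in Listing 9.

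In SAP 3.3 the fold-rise denominator is Day 1 at all time points: "where pre-vaccination value is always the result obtained at Day 1, prior to the priming vaccination". The table shells use the same denominator in the rows after dose 2.

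Models 1A to 2B (SAP 8.3.2) contain prime-boost type, boost dose, interval and two interactions. The adjusted versions add "age in years, sex (female, male), BMI (<30, ≥ 30), and prior receipt of seasonal influenza vaccine in the current season", and vaccination in the two earlier seasons. No titer enters any model. SAP 8.3.2 sits under the exploratory analyses, but SAP 8.1 points to it for the primary endpoints.

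**The concern.** A covariate measured before treatment, and correlated with the outcome, reduces the residual variance of a treatment contrast in a linear model. For boost formulation the treatment is dose 2, and the titer just before dose 2 is the natural candidate. Day 1 cannot play that role: SAP 8.3.1 expects little or no antibody then, so a Day 1 fold rise carries almost the same information as the raw titer.

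The contrast affected is the antigen-sparing one that SAP 4.4.4 describes. It is estimated from 27 or so subjects per arm, so lost precision matters. In addition, no HAI or Neut output gives a within-subject ratio of post-dose-2 to pre-dose-2 titer, or of Day 181 to Day 22 after dose 2, with a confidence interval. Two separate group GMT intervals cannot supply one.

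**Working it through.** **1. The plan's own figure.** Protocol Table 14 (SAP Table 8) gives minimum detectable differences in responder proportions. Its inputs are a two-sided likelihood ratio test, α = 0.05, 80% power and 27 per arm, from Protocol 11.4.3: "It is assumed that up to 10% of subjects (N=3) will be excluded from the per protocol analysis". Take G = 2n[H(x₁/n) + H(x₂/n) − 2H((x₁+x₂)/2n)] with H(p) = p ln p + (1−p) ln(1−p). Reject when G is at least the 95th percentile of χ² on 1 df, and sum the binomial probabilities of the rejection region. At the stated differences 0.32, 0.35, 0.38, 0.37 and 0.34, power is 0.816, 0.794, 0.805, 0.813 and 0.801. The table reproduces and is not in dispute. It concerns proportions; the plan gives no such figure for log titers.

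**2. Which groups identify the boost contrast.** Model 2A has six coefficients for six groups, so it is saturated. The boost-dose effect within each prime is the difference of group means, Group 2 minus 3 or Group 5 minus 6.

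**3. Gain with no assay floor.** Let ρ be the within-arm correlation of pre- and post-dose-2 log titers. It is not in the documents, so it is shown as a range. Unadjusted:

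MDD = (1.960 + 0.842) × SD × √(2/27) = 0.762 SD.

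Adjustment multiplies this by √(1−ρ²):

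| ρ | √(1−ρ²) | MDD (SD units) | CI narrower by | Effective n, 27/(1−ρ²) | Power at the unadjusted 80% MDD |
|---|---|---|---|---|---|
| 0 | 1 | 0.762 | 0% | 27 | 80% |
| 0.3 | 0.954 | 0.727 | 4.6% | 29.7 | 83.6% |
| 0.5 | 0.866 | 0.660 | 13.4% | 36.0 | 89.9% |
| 0.7 | 0.714 | 0.545 | 28.6% | 52.9 | 97.5% |

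Pooling both primes (54 against 54), 0.539 SD becomes 0.514, 0.467 and 0.385 at ρ = 0.3, 0.5 and 0.7.

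**4. Check by simulation.** With SD 1 and 27 per arm, the boost contrast averaged over primes has variance (1/4)(4/27) = 1/27, so its SE is 0.192. In 1,500 replicates per setting the SE fell from 0.192–0.193 to 0.184, 0.167 and 0.138 at ρ = 0.3, 0.5 and 0.7. The estimate stayed near its true value of 0.50 with and without the covariate. The matter is precision only.

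**5. Effect of the assay floor.** SAP 4.5.2 sets titers below 10 to 5. The pre-boost value was floored and put into steps, with ρ now the correlation before flooring. CI narrowing:

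| Pre-boost titers at floor | ρ = 0.3 | ρ = 0.5 | ρ = 0.7 |
|---|---|---|---|
| 50% | 3.6% | 10.3% | 21.4% |
| 80% | 2.3% | 6.5% | 13.1% |
| 95% | 1.0% | 2.8% | 5.4% |

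**6. Where the covariate must not be used.** For the prime and interval contrasts, the pre-dose-2 titer is itself an outcome. A six-arm simulation let the prime act on the later titer only through the pre-dose-2 titer. At ρ = 0.5 the prime effect went from −0.49 to about 0 once the covariate was added.

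**7. A change score is not a substitute.** With equal SDs its variance is 2(1−ρ) times that of the raw titer. At 27 per arm its MDD is 0.902, 0.762 and 0.591 SD at ρ = 0.3, 0.5 and 0.7. It beats the raw titer only above ρ = 0.5, and at all three values it is worse than adjustment.

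**The case against.** The best case for leaving the plan alone is that it has no formal hypothesis (Protocol 11.2; SAP 5 and 6.8), that its primary analysis is group summaries with intervals, and that the regression is exploratory. The gain may also be negligible. Protocol 2.1 describes avian-strain vaccines as poorly immunogenic. Protocol 2.2 says that the 2013 vaccine does not raise protective antibody against the newer lineage, which bears on Groups 2 and 3 tested against the 2017 virus. The pre-boost sample comes about four months after a single 3.75 mcg dose. A high share of titers below 10 is therefore plausible.

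The point about size stands, and the range above runs down to nil because of it. The point about purpose does not remove the concern: a study that aims at estimates gains from tighter ones, and SAP 8.3.2 says that it will test the treatment effects.

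A reader might go further in several ways that the documents do not support:

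- That the boost comparison is biased. It is not; Groups 2 v 3 and 5 v 6 are randomized and differ only in the boost.
- That the effect of the second vaccine is never isolated. The planned contrast already isolates boost formulation. Group GMTs before and after dose 2 are also both reported, so a crude ratio can be formed. Only the within-subject ratio with an interval is missing.
- That the pre-dose-2 titer is barely reported. It is shown with intervals across eight tables and four figures.
- That the durability objective is unmet. SAP 3.2.2 defines it through GMTs and response rates about 180 days after dose 2. A paired waning ratio would be an addition, and HAI or Neut fold rise is not a listed endpoint.

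**Conclusion.** The point holds as a free improvement in precision. The planned log-titer comparison of boost formulations is valid. It leaves out a pre-treatment covariate that the trial collects, assays and reports only descriptively. The benefit cannot be fixed from the documents: it depends on the pre/post correlation and on the share of pre-boost titers below 10, and both are assumed here. With no floor, intervals narrow by nothing at a correlation of 0 and by up to about 29% at 0.7. With 80–95% at the floor and correlations of 0.3 to 0.7, they narrow by about 1–13%. Confidence is high that the covariate is omitted, and low that the gain is large. The statement covers the linear models only. In the logistic models a prognostic covariate need not narrow the interval for the odds ratio.

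**What to change.** 1. In SAP 8.3.2, add a linear model in Groups 2, 3, 5 and 6 only. The outcome is log titer at Day 22, and separately at Day 181, after vaccination 2. The terms are boost dose, priming vaccine, their interaction and the log pre-dose-2 (Day 121) titer for the same assay and strain. Report only the boost-dose contrast from it. State that the covariate is not used for the interval or prime contrasts, and make no claim about odds-ratio intervals. Keep the existing models and the Day 1 definition of seroconversion.

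2. Optionally, as description, report the geometric mean fold rise from the pre-dose-2 sample and the Day 181 to Day 22 post-vaccination 2 ratio, each with a paired t interval. Footnote that the pre-dose-2 fold rise is not comparable between the 21-day and 120-day groups or between primes, because its denominator depends on both. Footnote also that setting titers below 10 to 5 can distort both ratios.

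The cost is SAP wording and eight model fits (two assays × two strains × two time points), with no new samples. Restricted to 4 × 27 = 108 subjects, the model spends one extra degree of freedom, leaving 103 instead of 104. It should be specified before unblinding, since Protocol 11.6 requires the SAP to be final by then.

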4. INVESTIGATIONAL PLAN

4.1. Overall Study Design and Plan

DMID Protocol 17-0078 follows a Phase II randomized, partially-blinded study design enrolling males and non-pregnant females aged 19 to 50 years of age, inclusive, who are in good health as determined by medical history and physical examination, and meet all eligibility criteria, including erythrocyte sedimentation rate (ESR), hematology, and biochemistry parameter within acceptable range, and negative urine or serum pregnancy test (for females). This clinical trial is designed to assess the safety, reactogenicity and immunogenicity of one or two vaccinations of monovalent inactivated split influenza 2013 and 2017 A/H7N9 virus vaccines (2013 and 2017 A/H7N9 IIVs) manufactured by Sanofi Pasteur (SP), administered intramuscularly at different dosages (3.75 or 15 mcg of HA per dose), given with or without AS03 adjuvant manufactured by GlaxoSmithKline Biologicals (GSK), using different heterologous and homologous prime-boost vaccination schedules.

Subjects will be randomly assigned to 1 of 6 study groups with equal allocation 1:1:1:1:1:1 (see [Table 1](#)). Subjects assigned to Groups 1, 2, and 3 will receive an adjuvanted 2013 A/H7N9 IIV on Day 1 while those in Groups 4, 5, and 6 receive an adjuvanted 2017 A/H7N9 IIV on Day 1. Subjects assigned to Groups 1 and 4 will return approximately 21 days after their first vaccination to receive an adjuvanted 2017 A/H7N9 IIV. Subjects assigned to Groups 2,3,5, and 6 will return approximately after 120 days to receive their second vaccination of 2017 A/H7N9 IIV with or without AS03.

Reactogenicity will be measured by the occurrence of solicited injection site and systemic reactions from the time of each study vaccination through 7 days after each study vaccination. Unsolicited non-serious AEs will be collected from the time of each study vaccination through approximately 21 days after each study vaccination. SAEs and MAAEs, including NOCMCs and PIMMCs, will be collected from the time of the first study vaccination through approximately 12 months after the last study vaccination. Clinical laboratory evaluations for safety will be performed on venous blood collected prior to each study vaccination and approximately 7 days after each study vaccination.

Immunogenicity testing will include performing HAI and Neut antibody assays against the influenza A/H7N9 study vaccine viruses on serum samples collected immediately on Day 1, Day 22 post vaccination 1, Day 121 post vaccination 1 for study groups 2,3,5,6, and on approximately Day 181 post vaccination 2.

Novel methods for identifying and assessing alternative correlates of protection against influenza infection are needed. To assess the NA specific antibody response to vaccination, it is first necessary to determine the NA content of inactivated influenza vaccine; this assay is under development. If successful, the NA content in a dosage specific manner can be correlated to the N9 NA-specific antibody responses elicited by the 2013 and 2017 H7N9 IIVs. The analyses for this exploratory endpoint will be described in an addendum to this SAP, if the assay becomes available.

4.2. Discussion of Study Design, Including the Choice of Control Groups

This study uses a dose comparison concurrent control design. Study subjects received either 2013 A/H7N9 IIV or 2017 A/H7N9 IIV with differing dosages with or without adjuvants and on differing administration schedules.

4.3. Selection of Study Population

The study population for this clinical trial is 180 males and non-pregnant females, 19 to 50 years of age, inclusive, who are in good health and meet all eligibility criteria. The subjects will be recruited from the general population at the participating Vaccine Trial and Evaluation Unit (VTEU) sites that have substantial experience conducting large influenza vaccine studies.

4.4.2. Identity of Investigational Product(s)

See the study protocol for details of study product formulation.

4.4.3. Method of Assigning Subjects to Study Groups (Randomization)

Enrollment/randomization will be performed through the enrollment module in the electronic data capture system, maintained by the SDCC.

Eligible subjects will be stratified by clinical site and prior receipt of seasonal influenza vaccine and randomly assigned with equal allocation (1:1:1:1:1:1) to 1 of 6 study groups indicated in [Table 1](#). The treatment sequence was generated using permuted block randomization to provide an approximately balanced allocation to the study groups during the study.

4.4.4. Selection of Doses in the Study

Subjects in Groups 1, 2, and 3 are to receive a first vaccination of AS03 adjuvanted 2013 A/H7N9 IIV at HA dose of 3.75mcg, and a second vaccination of either AS03 adjuvanted 2017 A/H7N9 IIV at HA dose of 3.75mcg (Groups 1 and 2) or unadjuvanted 2017 A/H7N9 IIV at HA dose of 15mcg (Group 3). Subjects in Groups 4, 5 are to receive two AS03 adjuvanted 2017 A/H7N9 vaccinations at HA doses of 3.75. Subjects in Group 6 are to receive a first vaccination of AS03 adjuvanted 2017 A/H7N9 IIV at HA dose of 3.75mcg, and a second vaccination of unadjuvanted 2017 A/H7N9 IIV at HA dose of 15mcg.

The 3.75 mcg with AS03 dose was selected to evaluate safety and immunogenicity of antigen sparing dose strategies compared to that of using a higher dose of 15 mcg without adjuvant. Using the 2013 and 2017 A/H7N9 IIVs allows the evaluation of priming effects of different A/H7N9 IIVs.

